## 10.8 Safety Analyses

### **10.8.1 Adverse Events**

Incidence of adverse events will be tabulated by MedDRA System Organ Class and preferred term within each system organ class. Serious adverse events and adverse events related to study drug will be summarized similarly. Ocular and non-ocular adverse events will be summarized separately.

---

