### **8.4.4 Post-Operative Day 8 (Visit 4, Day 8) Day 14 (Visit 5, Day 14) and Day 30 (Visit 6, Day 30)**

At the Day 8, Day 14 and Day 30 Visits, the following assessments will be performed:

- Prior and concomitant medication
- AEs (record incidence and severity of any adverse events that occur after the insertion)
- Distance visual acuity (VA)
- Best-Corrected Visual Acuity
- Ocular pain assessment (0 to 10)
- Slit lamp examination (including anterior chamber count and anterior chamber flare)
- Intraocular pressure
- Insert visualization

- MAC OCT Day 30
- Dry eye severity as measured by VAS on Day 8 and Day 30

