### **9.4 Monitoring and Recording of AEs and SAEs**

#### **9.4.1 Adverse Events**

Any AE experienced by the subject from the Screening/Baseline Visit after insertion of the DEXTENZA, through the 29-Day PostInsertion Visit is to be recorded in the CRF, regardless of the severity of the event or its relationship to study treatment.

Any AEs already documented at a previous assessment and designated as ongoing should be reviewed at subsequent visits, as necessary. If these have resolved, this should be documented.

Changes in intensity or frequency of AEs should be recorded as separate events (i.e., a new record started).

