#### **9.4.3 All Events**

All events must be assessed to determine the following:

- If the event meets the criteria for a SAE as defined in Section 9.2
- The severity of the event as defined in Section 9.7.1
- The relationship of the event to study treatment as defined in Section 9.7.2

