## 9.7 Evaluating AEs and SAEs

### 9.7.1 Severity

The following definitions should be considered when evaluating the severity of AEs and SAEs.

**Mild** Event is noticeable to the subject but is easily tolerated and does not interfere with the subject's daily activities.

**Moderate** Event is bothersome, possibly requiring additional therapy, and may interfere with the subject's daily activities.

**Severe** Event is intolerable, necessitates additional therapy or alteration of therapy, and interferes with the subject's daily activities.

For AEs that change in intensity, the start and stop date of each intensity should be recorded.

An AE that is assessed as severe should not be confused with a SAE. An event is defined as 'serious' when it meets one of the pre-defined outcomes as described in Section 9.2

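### The adverse event tables in section 10.8.1 do not use the severity grade and do not state a split by punctum or whether eyes, subjects or records are counted

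*Combined protocol and SAP*

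**What the plan says.** On collection, the protocol is thorough. Section 9.4.3 lists what must be assessed for all events, including "The severity of the event as defined in Section 9.7.1". Section 9.7.1 defines mild, moderate and severe by how well the event is tolerated, whether it needs therapy and whether it disturbs daily activities. It adds: "For AEs that change in intensity, the start and stop date of each intensity should be recorded". Section 9.4.1 says: "Changes in intensity or frequency of AEs should be recorded as separate events (i.e., a new record started". The visit lists in 8.4.1 to 8.4.4 repeat the instruction: "AEs (record incidence and severity of any adverse events that occur after the insertion".

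On reporting, section 10.8.1 is the whole AE analysis. Its main table is described thus: "Incidence of adverse events will be tabulated by MedDRA System Organ Class and preferred term within each system organ class". The subsets follow: "Serious adverse events and adverse events related to study drug will be summarized similarly". Ocular and non-ocular events are shown separately. Section 10.8.1 does not mention severity, punctum group or the unit counted. The Statistical Methods row of the synopsis says only that data are displayed overall, as applicable.

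**The concern.** AEs are one of two safety endpoints (6.2.2), and the objective in section 5 is a comparison of lower with upper punctum. Both groups receive the same insert (6.3), so a difference in safety could lie in how bad the events are as well as in how many eyes have one. Section 7.4.1 names the severity of AEs, alongside their incidence, as a possible reason to terminate the study. The study plans no formal testing (10.1, 10.3), so its tables are its whole result. A dimension that is recorded for every event but appears in no table will not reach the reader.

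The record-splitting rule adds a second difficulty. If records are counted, an event that fluctuates weighs more than one that stays severe throughout. If eyes or subjects are counted, that problem goes, but the grade still does not appear.

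**Working it through.** The documents state no figure to reproduce. The check compares what is collected with what is tabulated.

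**1. Collected against tabulated.**
- Severity grade: required for all events (9.4.3, 9.7.1, 8.4.1 to 8.4.4). In 10.8.1: not used.
- Change of intensity or frequency: a new record each time (9.4.1), with dates for each intensity (9.7.1). In 10.8.1: no rule for joining records.
- Assigned punctum: the randomized comparison (6.3). In 10.8.1: not mentioned. Synopsis: overall, as applicable.
- Unit: one or both eyes of a subject may be enrolled (7.1). In 10.8.1: eye, subject or record not stated.

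**2. Any other table that uses the grade?** None was found. In 10.7 severity refers to the dry eye visual analog scale, not to AEs.

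**3. Can another planned table stand in?**
- The serious-event table cannot, because 9.7.1 itself separates severe from serious. It shows severe events only when they are also serious.
- The related-event table cannot, because the criteria in 9.7.2 do not involve severity.
- Intraocular pressure (IOP) by visit (10.8.2), and cell, flare, pain and visual acuity (10.7), show the degree of some problems. Section 4.3.2 also lists insertion risks such as punctal trauma and canaliculitis, for which no graded measure other than the AE grade is planned.

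**4. Counting unit.** Take one event in one eye that goes mild, moderate, mild. Under 9.4.1 this gives 3 records. With 40 eyes in the group (the planned maximum, synopsis):
- counting eyes: 1/40 = 2.5%
- counting records against eyes: 3/40 = 7.5%

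Section 10.8.1 does not say which applies.

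**5. Illustration of the lost grade, with assumed counts.** Suppose the tables were shown by punctum and eyes were counted. Suppose also that 4 of 40 eyes in each group had the same related, non-serious preferred term.
- Planned layout: 4/40 = 10% versus 4/40 = 10%.
- If 1 of the 4 is severe in one group and all 4 in the other: 1/40 = 2.5% versus 4/40 = 10%.
- Full range: each group could have from 0 to 4 severe events, that is 0/40 = 0% to 4/40 = 10%. Every combination gives the same planned table.

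The documents give neither a severity distribution nor rates for insertion trauma or canaliculitis, so these counts are not a forecast. The 10% for anterior chamber inflammation in section 4.1 happens to match 4/40, but the degree of that event is partly measured by the cell and flare scores.

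**The case against.** **The SAP can add the table.** Section 10.1 promises a general SAP, and 10.9 lets it record changes. The grades and dates are recorded, so nothing is lost if a table is added before reporting. This stands, and it limits the point to a reporting omission that can be repaired. It does not remove the point: 10.8.1 already names specific tables, and no SAP text that adds severity is among the documents.

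**Incidence normally means participants with at least one event.** That is a fair reading and would avoid counting records. It still leaves eye or subject open in a study that allows both eyes, and it does not bring the grade into the table.

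**The degree of the commonest events is captured elsewhere.** This stands in part for inflammation and raised IOP (10.7, 10.8.2). It does not stand for insertion trauma, canaliculitis and similar events.

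**The table would rarely separate the groups.** For 1/40 versus 4/40, the two-sided Fisher p-value is 2 × [C(40,1)·C(40,4) + C(40,5)] / C(80,5) = 2 × (3,655,600 + 658,008) / 24,040,016 = 0.36. This is correct, but the study plans no tests. The purpose is to describe severity, not to prove a difference.

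**A stronger reading is tempting.** A reader might infer that the planned tables will show the two puncta as equally safe when one has worse events. The documents do not support this. No AE table by punctum is stated, and a count of one per eye is not stated either. The missing group split comes first: adding severity to an overall table would not serve the lower-versus-upper comparison.

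**Conclusion.** The point holds as an omission in the AE reporting plan. The listed tables leave out a grade that the protocol requires for every event, and they leave the group split and the counting unit open. The practical loss falls on severe, non-serious ocular events with no other graded measure, and on events with more than one record. The documents give no severity data, so the size cannot be estimated. The 2.5% versus 10% contrast hidden behind 10% versus 10% rests on assumed counts, 40 eyes per group, a display by punctum and a count of eyes. It would be wrong to infer that severity data are lost altogether, or that the degree of inflammation and raised IOP will go unreported. The primary efficacy results are unaffected. The change should be made before the tables are fixed.

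**What to change.** Add to section 10.8.1:

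> Ocular AEs are tabulated by assigned punctum, system organ class, preferred term and worst severity, counting each study eye once per preferred term at its worst grade. Records split under 9.4.1 because intensity or frequency changed are joined into one episode. The number and percentage of eyes with any moderate or severe ocular AE are shown for each group. Non-ocular AEs are tabulated per subject by worst severity, overall, and by punctum only for subjects whose study eye(s) share one assignment.

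The last sentence is needed because both eyes may be enrolled and 6.3 does not say whether they share an assignment. A subject with one eye in each group has no single punctum for a non-ocular event. The joining rule covers frequency as well as intensity because 9.4.1 splits records on both.

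The cost is one more table and a record-linking rule, with no new visits or procedures. The grades and dates are already collected. The protocol text does not say whether the case report form records the affected eye for each ocular event or links a new record to the one that it continues. Both should be confirmed before the rule is programmed.

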### 4.3.2 Risks

The following adverse reactions are typical adverse events that are known to be expected with the insertion procedure using a standard dilator and blunt, non-toothed forceps: eye pain and discomfort, tearing or epiphora (with or without mucopurulent discharge), eye inflammation, allergic reaction, dacrocystitis, canaliculitis, decreased/impaired visual acuity, stenosis (narrowing/closing of the punctum and/or canaliculus), perforation of or trauma to the punctum and/or surrounding tissues, inability to remove test article, need for surgery on the lacrimal system, infection or intraocular infection that if severe could lead to temporary or permanent impairment of eye sight.

Additionally, based on several decades of use of topical ocular corticosteroids, risks have been identified with the use of dexamethasone, some of which have been observed in clinical trials with the DEXTENZA 0.4 mg dexamethasone insert. The following AEs and/or risks have been observed with the administration of corticosteroids: IOP increase/glaucoma/ocular hypertension, masking of infection or enhancing existing infections, delayed healing, cataracts. Other common risks (occurring in  $\geq 1\%$  of safety population) included anterior chamber inflammation, iritis, visual acuity reduced, corneal oedema, cystoid macular oedema, conjunctival hyperemia, eye pain, ocular discomfort, posterior capsule opacification, intraocular pressure increased, and corneal abrasion.

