### 9.7.2 Relationship to Investigational Procedure

The following definitions should be considered when evaluating the relationship of AEs and SAEs to the study treatment:

**Unrelated** This category applies to those (S)AEs which, after careful consideration, are clearly and incontrovertibly due to extraneous causes (disease, environment, etc.); there is no reasonable probability that the (S)AE may have been caused by the procedure or the product. If the Investigator determines that the AE is unlikely to be related to the study drug or procedure, then this would be the appropriate category.

**Related** The following criteria should be applied in considering inclusion of a (S)AE in this category:

- a. It bears a reasonable temporal relationship to the procedure or the presence of DEXTENZA.
- b. It could not be reasonably explained by the known characteristics of the subject's clinical state, environmental or toxic factors, or other factors (e.g., disease under study, concurrent disease(s), and concomitant medications) and modes of therapy administered to the subject
- c. It disappears or decreases on removal of the IP
- d. It follows a known pattern of response to the procedure or the product

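### One causality rating covers insertion procedure or product (9.7.2), but 10.8.1 tabulates it as related to study drug, with no procedure-related table

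*Combined protocol and SAP*

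**What the plan says.** Section 9.4.3 lists what must be assessed for every event. One item concerns causality: "The relationship of the event to study treatment as defined in Section 9.7.2".

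Section 9.7.2 is headed "Relationship to Investigational Procedure" and offers two categories. Unrelated requires that "there is no reasonable probability that the (S)AE may have been caused by the procedure or the product". Two of the four criteria for Related name both causes as alternatives: "It bears a reasonable temporal relationship to the procedure or the presence of DEXTENZA" and "It follows a known pattern of response to the procedure or the product".

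Section 10.8.1 plans these tables:
- All events: "Incidence of adverse events will be tabulated by MedDRA System Organ Class and preferred term within each system organ class".
- Serious and related events: "Serious adverse events and adverse events related to study drug will be summarized similarly".
- Ocular and non-ocular events, summarised separately.

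It names no table of procedure-related events and does not say that any event table is split by punctum.

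Section 4.3.2 has two risk lists. The first gives events described as "typical adverse events that are known to be expected with the insertion procedure using a standard dilator and blunt, non-toothed forceps". The second gives risks of corticosteroids and other common risks.

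**The concern.** The item that is collected and the table that is planned do not have the same scope. The rating answers whether the procedure or the product caused the event. The table claims to answer whether the drug did. A reader of the final report would take the table at its label and could attribute insertion injuries to dexamethasone.

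The design makes the distinction worth having. Under section 6.3 every subject receives the insert, and randomisation decides only whether it goes into the lower or the upper punctum. Section 5 sets the comparison of safety between the two placements as an objective. Harm from entering the punctum is tied directly to what is randomised, yet the plan has no display that isolates it.

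**Working it through.** No arithmetic is needed to establish the mismatch. It follows from setting the sections side by side.

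**1. How many causality items are recorded?** Section 9.4.3 requires one, by reference to 9.7.2. No other causality item is defined in the protocol.

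**2. What does that item measure?** Either cause. Unrelated excludes both the procedure and the product, and criteria a and d of Related accept either one. A Related rating therefore does not say which cause was meant.

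**3. Could study drug be shorthand for both causes?** The protocol's own usage is against it. The Unrelated definition in 9.7.2 names study drug and procedure as alternatives, and section 7.4 likewise separates the trial material from the insertion procedure. The single item goes by three names: procedure in the 9.7.2 heading, study treatment in 9.4.3 and study drug in 10.8.1.

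**4. Which procedure?** Section 9.7.2 does not say. Section 8.4.2 places both the cataract surgery and the insertion on Day 0, so a rater could have either in mind.

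**5. Can preferred terms recover the cause?** In part, judging from the two lists in 4.3.2:

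| Event | Insertion list | Corticosteroid / other common risks list |
|---|---|---|
| Punctal perforation or trauma | yes | no |
| Punctal or canalicular stenosis | yes | no |
| Canaliculitis | yes | no |
| Eye pain | yes | yes |
| Ocular discomfort | yes | yes |
| Reduced visual acuity | yes | yes |

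The first three can be picked out by term. The last three cannot.

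**6. Can a size be given?** No. The documents give no rate of insertion events, and the reaction rates in section 4.1 are not divided by cause. Suppose, purely as an assumption, that 2%, 5% or 10% of eyes have an insertion event rated Related, that events do not overlap, and that the inflation factor is (base + insertion) / base.
- Base = 6% (raised IOP alone): 8/6 = 1.33, 11/6 = 1.83, 16/6 = 2.67.
- Base = all seven rates in 4.1, 10 + 6 + 2 + 1 + 1 + 1 + 1 = 22%: 24/22 = 1.09, 27/22 = 1.23, 32/22 = 1.45.

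The answer depends on the base chosen and on an invented insertion rate, and neither base is a clean drug rate. None of these factors should be reported as a finding.

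**The case against.** The strongest reply is that this is a labelling slip in a descriptive study. Section 9.4.1 records every event whatever its relationship, and 10.8.1 tabulates all events by preferred term, with ocular events separate. Punctal trauma, stenosis and canaliculitis will be visible there by name. Section 10.7 also summarises insertion attempts and ease of insertion. Section 10.1 promises a general SAP that may define the table, and the CRF is not among the documents, so it may hold more than 9.4.3 requires.

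Much of this stands, and it rules out several stronger readings that a reader might infer:

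- *That insertion harm has no table at all.* It has no procedure-related table, but it is counted in the all-event and ocular tables.
- *That insertion harm is the only harm that can differ by punctum.* No section says so. IOP is a separate safety endpoint, and retention is recorded and could differ too.
- *That any given insertion injury will be rated Related.* Section 9.7.2 does not say whether criteria a to d must all be met or whether one is enough. Criterion c, improvement on removal of the product, need not hold for a perforation.
- *That the planned table will show a false drug difference between the groups.* That would need a display by group. Section 10.8.1 specifies none, and the synopsis speaks of showing data overall where applicable.

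The core of the reply does not stand. A later SAP can retitle a combined rating, but it cannot recover a distinction that was never recorded. For eye pain, discomfort and reduced acuity, the preferred term does not supply it either.

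**Conclusion.** The mismatch between 9.7.2 and 10.8.1 is real. As written, events caused by insertion and rated Related would enter a table labelled as drug-related, and no procedure-related table is planned. No magnitude can be derived from the documents.

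The conclusion assumes that the single rating in 9.7.2 is what fills the 10.8.1 table, since no other is defined, and that the CRF carries no further causality field. It does not depend on how criteria a to d combine, because neither reading separates the causes. The primary endpoints are unaffected. The change is worth making because it serves the stated comparison of safety by punctum, and it has to be in place before events are rated.

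**What to change.** - In 9.7.2, 9.4.3 and the adverse event CRF, replace the single rating with two yes/no items per event: related to the insertion procedure, and related to the dexamethasone insert. Allow both to be yes.
- State in 9.7.2 that procedure means the insertion and not the cataract surgery.
- In 10.8.1, replace the single related-event table with a procedure-related table and an insert-related table, each displayed by randomised punctum. The display by punctum has to be written in, because splitting the rating alone would not provide the comparison.
- If the CRF cannot change, retitle the table *related to study drug or insertion procedure*. This corrects the label but does not separate the causes.

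The cost is one extra CRF field per adverse event and one extra table. No additional visits, staff or patients are needed.

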### **10.8.2 IOP**

The observed values and change from baseline values for IOP will be summarized by visit.

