## 2 SYNOPSIS

Protocol Title	A randomized, controlled study to evaluate the safety and effectiveness of treatment with an intracanalicular dexamethasone (0.4mg) insert in the operating room following cataract surgery/intraocular lens implant (IOL) with or without iStent/Hydrus/Goniotomy when placed in the lower punctum compared to the upper punctum.
Phase of Clinical Study	Phase 4, Collaborative Study ✓
Investigational Product	DEXTENZA (dexamethasone ophthalmic insert, 0.4mg) for intracanalicular use
Study Objective	To assess the safety and effectiveness of treatment with an intracanalicular dexamethasone (0.4mg) insert in the operating room following cataract surgery/intraocular lens implant (IOL) with or without iStent/Hydrus/Goniotomy when placed in the lower punctum compared to the upper punctum.
Efficacy and Safety Endpoints	
Primary Efficacy:
 
 
• Absence of anterior chamber cells at Day 14 as measured by Summed Ocular Inflammation Score (0 to 4)
 
• Absence of ocular pain at Day 8 as measured by ocular pain assessment numerical grading scale (0 to 10)
 
 
Secondary Efficacy:
 
 
• Mean change in BCVA from Baseline
 
• Number and percentage of subjects with complete absence of pain
 
• Number and percentage of subjects with complete absence of cell
 
• Measuring cell, pain, and flare on Day 8, 14, 30
 
• Physician ease of insertion and visualization
 
• Number of attempts to successfully insert Dextenza
 
• Dry eye severity as measured by VAS at baseline, Day 8 and Day 30
 
• Record insert retention up to 30 days
 
 
Safety:
 
 
• Adverse events (AEs)
 
• Intraocular pressure (IOP)
 

Number of Sites	Single site, United States (US)

The SPENCER Study

Number of Subjects Planned	Up to 80 eyes; at least 60 eyes
Study Population	Subjects undergoing non-complicated CCI CE/PCIOL in one or both eyes with or without iStent/Hydrus/Goniotomy.

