## **5 TRIAL OBJECTIVES**

The study objectives are to evaluate the safety and effectiveness of treatment with an intracanalicular dexamethasone (0.4mg) insert in the operating room following cataract surgery/intraocular lens implant (IOL) with or without iStent/Hydrus/Goniotomy when placed in the lower punctum compared to the upper punctum.

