### **6.2.2 Safety Endpoints**

- Adverse events (AEs)
- Intraocular pressure (IOP)

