### **6.3 Randomization and Masking ✓**

This is an open-label study. All subjects will receive DEXTENZA. Subjects will be randomized to one of two treatment groups. Group 1 will receive the insert in the lower punctum on the day of surgery in the OR and Group 2 will receive the insert in the upper punctum on the day of surgery in the OR.

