## 8.4 Study Assessment by Visit

### 8.4.1 Screening/Baseline Visit (Visit 1, Day -21 to -1)

At the Screening/Insertion Visit (Visit 1, Day -1), the following assessments will be performed. Ocular assessments will be performed in each eye:

- Informed consent
- Inclusion/exclusion criteria
- Demographics
- Medical and ocular history
- Prior and concomitant medications (record any medication that subject is taking as well as those taken in the previous 60 days)
- AEs (record incidence and severity of any adverse events that occur after the insertion)
- Distance VA
- Best-Corrected Visual Acuity
- Ocular pain assessment (0-10)
- Slit Lamp Examination (including anterior chamber cell count, and anterior chamber cell flare)
- Punctum examination (size and presence of any punctal plug)
- Grade cataract density (scale 1 to 4)
- Intraocular pressure
- Dilated fundus exam
- IOL measurement
- MAC OCT
- Dry eye severity as measured by VAS

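### Section 10.8.2 summarises IOP by visit but names no lower-versus-upper estimate; a baseline-adjusted difference would give one, usually with better precision

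*Combined protocol and SAP*

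**What the plan says.** Section 6.2.2 lists two safety endpoints, adverse events and IOP. Section 5 sets a comparative objective, safety and effectiveness "when placed in the lower punctum compared to the upper punctum", and section 6.3 randomises: "Subjects will be randomized to one of two treatment groups". The Synopsis gives the size as "Up to 80 eyes; at least 60 eyes", with up to 40 eyes per group.

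IOP is in the baseline list of section 8.4.1, where "Ocular assessments will be performed in each eye". It is also in the list of section 8.4.4 that opens "At the Day 8, Day 14 and Day 30 Visits, the following assessments will be performed". It is not in the Day 1 list of section 8.4.3.

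The IOP analysis in section 10.8.2 is one sentence: "The observed values and change from baseline values for IOP will be summarized by visit". It mentions neither punctum group nor a difference between groups, an interval or an adjustment. The Statistical Methods row of the Synopsis speaks only of overall display where applicable. Sections 10.1 and 10.3 make all summaries descriptive. Section 10.1 foresees a brief SAP on data presentation, but nothing in the documents adds a between-group IOP estimate.

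**The concern.** The objective asks how IOP compares between the puncta, and section 10.8.2 does not say which number answers that. If the summaries are broken down by group, a reader can subtract observed means or subtract mean changes. The two answers differ whenever the groups differ at baseline by chance, and nothing in the plan says which to prefer. Section 6.3 describes no stratification. The groups are small, and eyes having iStent, Hydrus or goniotomy are mixed with eyes having cataract surgery alone, so some baseline spread is to be expected.

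At stake is the clarity and precision of one safety comparison. A post hoc choice between two numbers is weaker evidence than one named in advance, and a baseline value that is collected anyway would go unused in the comparison.

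**Working it through.** The plan gives no IOP figure to reproduce: section 10.2 reports no sample size calculation, and no SD, correlation or IOP difference of interest appears.

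**Inputs from the documents.** 60 to 80 eyes in total; up to 40 per group; IOP at baseline and on Days 8, 14 and 30.

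**Assumptions.** IOP SD s of 2.5 to 4 mmHg, equal at baseline and follow-up; baseline/follow-up correlation ρ of 0.3 to 0.7; independent eyes; equal split, so 30 per group at the 60-eye minimum. The 1 mmHg mark is only a yardstick.

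**1. Two possible answers.** With complete data,

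observed-value difference − change difference = baseline difference.

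This is an identity. Given a chance baseline gap g, the observed-value difference is shifted on average by ρg and the change difference by −(1−ρ)g. At ρ = 0.5 and g = 1 mmHg the shifts are +0.5 and −0.5 mmHg.

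**2. Size of the gap.** SE of the baseline difference = s√(2/n). The chance that it exceeds 1 mmHg in either direction is 2[1 − Φ(1/SE)].

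| s (mmHg) | n = 40: SE, chance | n = 30: SE, chance |
|---|---|---|
| 2.5 | 0.56, 7% | 0.65, 12% |
| 3 | 0.67, 14% | 0.77, 20% |
| 3.5 | 0.78, 20% | 0.90, 27% |
| 4 | 0.89, 26% | 1.03, 33% |

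In 20,000 simulated trials per setting with no true difference, the two unadjusted differences had opposite signs in about 29% to 37% of trials for ρ from 0.3 to 0.7.

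**3. Precision.** The 95% half-width is t(0.975, 78) × s × k × √(2/40), with k = 1 for observed values, √(2(1−ρ)) for change and √(1−ρ²) for the adjusted difference. With s = 3.5 and t = 1.99, the common factor is 1.99 × 3.5 × 0.2236 = 1.56 mmHg.

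| ρ | Observed | Change | Adjusted | Variance saved against the better unadjusted |
|---|---|---|---|---|
| 0.3 | 1.56 | 1.84 | 1.49 | 1 − 0.91 = 9% |
| 0.5 | 1.56 | 1.56 | 1.35 | 1 − 0.75 = 25% |
| 0.7 | 1.56 | 1.21 | 1.11 | 1 − 0.51/0.60 = 15% |

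ρ = 0.5 is the most favourable row, because the two unadjusted summaries tie there.

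**4. When adjustment helps.** Estimating the slope multiplies the adjusted variance by about f = 1 + 1/(N−4), which adds less than 1% to the half-widths above.

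- It beats observed values when (1−ρ²)f < 1, that is, ρ > √(1 − 1/f).
- It beats change when (1−ρ²)f < 2(1−ρ), that is, ρ < 2/f − 1.
- For N = 80, f = 1 + 1/76 and the range is about 0.11 to 0.97.
- For N = 60, f = 1 + 1/56 and the range is about 0.13 to 0.96.

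Outside these limits the adjusted estimate is level with the better unadjusted one or negligibly worse.

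**The case against.** The strongest reply is that the trial is declared descriptive, and that observed values with change from baseline are a coherent descriptive safety summary. Shown by group with the baseline visit, they would reveal any imbalance. That stands: the plan contains no error of calculation or logic here. It does not remove the comparative objective, and an estimate with an interval stays within a descriptive plan.

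A reader might infer that the plan contains two tables that contradict each other. The documents do not support this. Section 10.8.2 states no by-group display and no difference, so the two answers are ones that a reader would derive. The first gap is the missing by-group comparison; adjustment is the better way to fill it.

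A reader might also infer that both unadjusted summaries are always less precise, or that observed values carry the whole baseline imbalance. Neither holds. The precision gain needs a correlation inside the limits above, and observed values carry ρ times the imbalance, all of it only at ρ = 1. Under randomisation neither unadjusted difference is biased over repeated trials; the issue is chance imbalance in the one trial run.

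Three further limits stand. The mmHg figures rest on assumed inputs. They treat eyes as independent, although both eyes of a subject may be enrolled, so the actual half-widths may differ. And the documents describe IOP risk largely as events (section 4.1 reports increased IOP in 6%), about which a mean difference says little.

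**Conclusion.** The point holds as a modest, optional improvement. Section 10.8.2 leaves the lower-versus-upper IOP comparison unnamed, and a value already collected would supply one estimate that does not depend on which summary a reader picks.

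Its size depends on figures that the documents do not give. Over an SD of 2.5 to 4 mmHg, the two derivable answers would differ by more than 1 mmHg in roughly 7% to 33% of trials, depending on SD and group size. The precision gain over the better unadjusted summary is small to moderate: at SD 3.5 mmHg and 40 eyes per group, 0.07 mmHg of half-width at ρ = 0.3, 0.21 at ρ = 0.5 and 0.10 at ρ = 0.7. These figures assume equal SDs, complete data and independent eyes. They do not show that the IOP conclusion would be wrong under the present plan.

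**What to change.** In section 10.8.2, or in the SAP as section 10.9 allows:

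- State that IOP will be shown by punctum group at each visit, baseline included.
- Name as the IOP comparison the lower-minus-upper difference in mean IOP at Days 8, 14 and 30, each with a 95% confidence interval, from a linear model with punctum group and baseline IOP.
- Cluster standard errors by subject where both eyes are included.
- Present it as descriptive estimation without a p-value.
- Keep the observed-value and change summaries as supporting tables.

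The cost is a few lines of text and one simple model per visit. It needs no new assessment, no extra eyes and no formal test. The mean difference does not replace the reporting of individual IOP elevations, which should continue alongside it.
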